### **7.11.2 Laboratory Data**

Descriptive statistics of the observed values and change from baseline (continuous data) will be presented by treatment group and visit for each hematology, urinalysis and serum chemistry parameter. Each measurement (continuous data) will be classed as below, within, or above normal range, based on ranges supplied by the laboratory used. Shift tables in relation to the normal range from baseline to each follow-up visit will be presented.

### **7.11.3 Vital Signs**

Descriptive statistics for observed values and changes from baseline in the following vital signs will be presented by treatment group and visit:

- Systolic blood pressure (mmHg)
- Diastolic blood pressure (mmHg)
- Pulse rate (bpm)
- Respiration rate (breath/min)
- Body temperature (degrees Celsius)
- Body weight (kg).

#### **7.11.4 Electrocardiogram Data**

Overall ECG interpretation (Normal, Abnormal NCS, and Abnormal CS) data will be summarized by visit and treatment. Additionally, shift tables in relation to the overall interpretation from baseline to each follow-up visit will be presented.

#### **7.11.5 Physical Examination**

Physical examination data will be listed.

#### **7.11.6 Local Tolerability**

##### ***7.11.6.1 Injection Site Discomfort Assessments***

Descriptive statistics for observed Visual Analog Scale (VAS) Score (mm; measure of discomfort) for injection Site discomfort will be presented by timepoint (10, 30, 60 and 180 minutes post-injection), visit and treatment group.

Number (percent) of subjects who had any discomfort when the pump administered study drug presented by visit and treatment group. For those with any discomfort, Incidence of type of discomfort (Categories: Pain; Itching; Tingling, twitching or numbness; Irritation (e.g., burning, stinging) and how long after study drug administration did the discomfort start (less than 1 minute, 1-2 minutes, 3-5 minutes, 6-9 minutes, at least 10 minutes) and Descriptive statistics for how long did the discomfort last (minutes) will be presented by visit and treatment group.

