### **6.1.2.3. Glucagon Infusion Rate Selection**

A previous study (Edelman, ADA annual scientific sessions, 2006) evaluating continuous glucagon administration for the prevention of hypoglycemia tested doses at 2, 4 and 8 ng/(kg\*min) and found apparently no effect at 2 ng/(kg\*min), weak indications of effect at 4 ng/(kg\*min) and, given a modest sample size, reasonably clear effect at 8 ng/(kg\*min) with some but limited room for further effect.

These findings would suggest doses in the vicinity of 4 and 16 ng/(kg\*min) corresponding to 19.2 and 76.8 µg/hr for an 80-kg person would be well chosen in this proof-of-concept study. As further development would most likely lead to a device with a fixed infusion rate, the glucagon doses chosen for the study are 20 and 80 µg/hr, or given the formulation concentration of 5 mg/ml, infusion rates of 4 and 16 µl/hr. For the pump setting that measures in insulin U100 units that corresponds to 0.4 and 1.6 U/hr.

This highest dose to be tested in the study will allow a greater than 10x safety margin based on findings from a 28-day toxicology study in rats conducted with Xeris glucagon (see current Investigator's Brochure).

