## 7. STUDY DESIGN

### 7.1. Study Overview

This is a prospective, randomized, double-blind, parallel trial with the primary analysis after 4 weeks treatment with CSGI or placebo. As both the low and high dose group use the same formulation, the dose will be determined by infusion. To preserve the blind, the placebo therefore is administered by matching infusion methods to CSGI (high and low infusion rates, split to create the appearance of a 4-group trial on the schematic).

Study Schematic:

After a 1-week run-in on CGM, subjects will have key hormones of their hypoglycemia counter regulatory response quantified using a stepwise hypoglycemia induction. They will then receive investigational product for 4 weeks before discontinuation and reassessment of the same hypoglycemia counter regulatory response.

Treatment stops at 4 weeks, but subjects will continue blinded for 6 additional months to investigate duration of response with assessments at 3 and 6 months. The primary endpoint will be tested at 4 weeks post randomization, but the double blind will remain intact until the end of the study.

Baseline Qualification:

Subjects will continue their insulin regimen as usual throughout the study, adjusted by the investigator to achieve ADA recommended targets.

After enrollment, the subjects will require approximately one week of CGM data prior to their baseline hypoglycemia induction procedure. Subjects will enter a run-in phase of 1 week wearing a blinded CGM device.

Subjects will arrive in the Clinical Research Unit (CRU) the morning of the planned hypoglycemia induction procedure. The CGM data will be retrieved. The following CGM criteria must be met: a minimum of 6 days must be recorded using the CGM before the subject will be fitted with a new CGM device. If the CGM criteria are not met, the subject is inserted with another CGM for renewed baseline period. Should the second baseline period not yield eligible CGM data, the subject will stop further participation in the screening procedures.

The subject will fast after midnight. The subject's arms are cannulated venously, one side for both insulin and glucose infusion and the other side for venous sampling. The subject will stop their own insulin treatment and receive IV insulin and IV glucose to maintain their plasma glucose between 80 to 120 mg/dL, as measured by either BGM or YSI. They will remain fasting until the end of the hypoglycemia procedure the following day.

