##### **8.6.1.2. Matching Placebo**

The placebo consists of the vehicle for CSI-Glucagon, so it contains DMSO and trehalose, but no glucagon. The placebo is indistinguishable from the investigational drug and will be stored under the same conditions.

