**11.3.6. Local Tolerability:**

The incidence of any injection site discomfort (score >0 on the ordinal rating scale) will be analyzed descriptively. The incidences of erythema and edema will be analyzed in a similar manner. Descriptive statistics (only) will be provided for time of onset and duration (of discomfort) and discomfort description (i.e., pain, irritation, itching, etc.). Mean VAS scores will be compared between the treatments.

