### **6 RANDOMIZATION**

The randomization scheme is 1:1:1 for high dose, low dose and placebo. Each group will have 16 subjects, but the placebo group will be matched to high and low infusion rates (8 in each group). The randomization is stratified by site.

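### Local tolerability tables set each CSGI dose against one placebo column that pools two vehicle infusion rates, so neither dose column is matched to placebo on vehicle volume

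*SAP*

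**What the plan says.** Dose is set by pump rate, not by strength. Protocol 7.1: "As both the low and high dose group use the same formulation, the dose will be determined by infusion". Protocol 6.1.2.3 states that "the glucagon doses chosen for the study are 20 and 80" µg/hr and, "given the formulation concentration of 5 mg/ml, infusion rates of 4 and 16" µl/hr. On the U100 pump scale "that corresponds to 0.4 and 1.6 U/hr".

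Placebo is the vehicle alone, "so it contains DMSO and trehalose, but no glucagon" (Protocol 8.6.1.2). Randomization is 1:1:1 with 16 per group, and "the placebo group will be matched to high and low infusion rates (8 in each group") (SAP 6). Protocol 7.1 gives blinding as the reason for matching the placebo rates.

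The table columns in SAP 7.3.2 are CSGI Low, CSGI High, CSGI Combined, one Placebo column and Total. SAP 7.11.6.1 says that VAS scores "will be presented by timepoint (10, 30, 60 and 180 minutes post-injection), visit and treatment group". The discomfort questionnaire and the Draize scores (SAP 7.11.6.2) are also summarized by treatment group. None of the titles of Tables 14.3.7.2.1 to 14.3.7.2.4 in SAP 12 mentions the placebo rate. The SAP plans descriptive summaries only. Protocol 11.3.6 goes a little further: "Mean VAS scores will be compared between the treatments", with no test named.

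**The concern.** Local discomfort, erythema and edema can come from the glucagon, from the vehicle, or from both. Raising the dose four-fold also raises the vehicle volume four-fold, so the high-versus-low contrast cannot separate the two sources. Placebo can separate them, but only if it runs at the same rate as the dose it is set against. A pooled Placebo column sits between the two rates and matches neither dose.

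If reactions rise with volume, the high dose would look worse than placebo and the low dose better, even if glucagon added nothing locally. That pattern is easily read as a dose-related drug effect.

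These tables carry most of the local safety evidence. Under Protocol 10.6 an injection site reaction is not an adverse event unless it needs medical intervention, so milder reactions will not appear in the adverse event tables.

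**Working it through.** **1. The plan's own rates.** Rate = dose / concentration, with 5 mg/ml = 5 µg/µL. Low: 20 / 5 = 4 µL/h. High: 80 / 5 = 16 µL/h. Both reproduce the protocol's figures, and the ratio is 4.

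**2. Mean vehicle rate per table column**, from the planned allocation:

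| Column | Mean vehicle rate (µL/h) | Minus placebo | Ratio to placebo |
|---|---|---|---|
| Placebo, pooled | (8×4 + 8×16)/16 = 10 | – | – |
| CSGI Low | 4 | −6 | 0.4 |
| CSGI High | 16 | +6 | 1.6 |
| CSGI Combined | (16×4 + 16×16)/32 = 10 | 0 | 1.0 |

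**3. What the mismatch does to a difference in means.** Let f(4) and f(16) be the mean score on vehicle alone at each rate. Pooled placebo estimates [f(4) + f(16)]/2. High minus pooled placebo then equals the glucagon effect at the high rate plus [f(16) − f(4)]/2. Low minus pooled placebo equals the glucagon effect at the low rate minus the same quantity. In Combined minus pooled placebo the two terms cancel, whatever the shape of f.

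The documents give no value for f(16) − f(4). Assume a linear slope of b mm VAS per µL/h. Then f(16) − f(4) = 12b, and the shifts are +6b (high) and −6b (low):

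| b | High minus placebo | Low minus placebo |
|---|---|---|
| 0 | 0 mm | 0 mm |
| 0.5 | +3 mm | −3 mm |
| 1 | +6 mm | −6 mm |
| 2 | +12 mm | −12 mm |

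**4. Vehicle delivered at one site when each measure is taken** (rate × time):

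| Measure | Low rate | High rate |
|---|---|---|
| VAS and questionnaire, 10 min | 4×10/60 = 0.7 µL | 16×10/60 = 2.7 µL |
| VAS, 180 min | 4×3 = 12 µL | 16×3 = 48 µL |
| Draize after pod removal, 48 h wear | 4×48 = 192 µL (0.19 mL) | 16×48 = 768 µL (0.77 mL) |

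The protocol has pods changed every 2–3 days; 48 h is the lower end. The 10-minute measures are least exposed to a volume effect and Draize is most exposed.

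**5. If the achieved placebo split is uneven.** From 6 high/10 low to 10 high/6 low, the pooled mean runs from (6×16 + 10×4)/16 = 8.5 to (10×16 + 6×4)/16 = 11.5 µL/h. Both doses stay unmatched.

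**6. Precision after a split**, assuming a common SD. Dose (16) minus pooled placebo (16): SE = SD×√(1/16 + 1/16) = 0.354 SD. Dose (16) minus rate-matched placebo (8): SE = SD×√(1/16 + 1/8) = 0.433 SD. The ratio is √1.5 = 1.22. The average of the two matched differences has SE = SD×√[2(1/16 + 1/8)]/2 = 0.306 SD, the same as Combined minus pooled placebo, SD×√(1/32 + 1/16) = 0.306 SD.

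**The case against.** The strongest reply has five parts.

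- **Purpose of the split.** A reader might infer that placebo was divided to give each dose its own vehicle control and that the SAP throws this away. The documents do not support that. Protocol 7.1 makes the split to protect the blind, and neither document plans a rate-matched comparison. The SAP therefore breaks no promise. The matched subjects nevertheless exist.
- **No demonstrated bias.** A reader might also take it as established that vehicle volume distorts the dose comparisons. The documents give no volume-response for discomfort, erythema or edema. If volume has no effect, the bias is zero. This stands, and the point is conditional.
- **Exposure.** Multiplying the rates over 28 days (16×24×28 = 10.75 mL vs 4×24×28 = 2.69 mL) suggests a large contrast, but that total is spread over many sites and no tolerability measure reads it. The relevant volumes are those in step 4 of the working.
- **A balanced contrast is already planned.** Combined CSGI against pooled placebo has the same mix of rates on both sides, and each CSGI column's own values are unaffected. This stands too. It does not help a reader of the separate dose columns, which the SAP also shows.
- **Descriptive tables and small cells.** The SAP names no test, and it supersedes the protocol's statistical text. With 8 per cell, one subject is 12.5 percentage points, and 0 of 8 has an exact 95% upper limit of about 37%. Split columns will be imprecise.

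The mock table shells mentioned in Protocol 11 are not among the documents, so the final layout cannot be confirmed. The general rule in SAP 7.3.2 is the only layout stated.

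**Conclusion.** The point holds as a matter of presentation, and it is minor. As planned, the high-dose column is set against placebo at 1.6 times its mean vehicle rate and the low-dose column at 0.4 times. Combined CSGI is balanced. If site reactions rise with vehicle volume, the separate dose columns overstate the local effect of glucagon at the high dose and understate it at the low dose, each by half the difference between the two placebo rates. The shifts in mm rest on an assumed linear slope, and they are zero if there is no volume effect. The working uses the planned 8/8 split. Draize after pod removal is the most exposed measure, and the 10-minute VAS and questionnaire are the least. The epinephrine analysis is outside this point.

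**What to change.** In Tables 14.3.7.2.1 to 14.3.7.2.4, add two placebo columns, 4 µL/h and 16 µL/h, and place each beside the dose given at that rate. Keep the pooled Placebo and Combined CSGI columns. State in SAP 7.11.6 that dose-specific local tolerability is read against the rate-matched placebo. Leave pooled placebo in place for the epinephrine endpoint.

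The two placebo columns also show directly whether vehicle volume matters, which decides how far the pooled column can be trusted.

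The cost is extra columns in four tables, with no new data. Each matched placebo cell has 8 subjects, and the SE of a dose-minus-placebo mean difference rises from 0.354 SD to 0.433 SD. No planned test loses power, because the SAP specifies none here. The four tables carry no asterisk in SAP 12, so they are not part of the Day 27 primary endpoint package, and the split adds nothing to what is unblinded at that stage.

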##### ***7.11.6.2 Draize Scale***

Incidence of erythema will be presented by summarizing the Draize Scale Score for Erythema Formation by time point, visit and treatment group. The incidence if edema will be summarized similarly based on the Draize Scale Score for Edema Formation.

A shift table comparing Week 1, 10 minutes post-dose to Week 1, 60 minutes post-dose and Week 4, 10- and 60-minutes post-dose scores will be presented by treatment group.

### **8 INTERIM ANALYSIS**

No interim analyses are planned. However, the primary endpoint analysis at Day 27 will be executed when the last subject data for this visit has been completed and monitored. Primary endpoint analysis results will only be unblinded at the treatment group level (CSGI high dose, CSGI low dose, placebo) and individual treatment assignments will remain blinded until the end of the study and the final database locked. Study investigators, study staff, subjects and the sponsor will remain blinded to individual group assignments. Primary endpoint analysis is defined as all analyses that include the evaluation of epinephrine (both primary and secondary designated analyses) and other corresponding counter regulatory hormones (norepinephrine, cortisol, glucagon and growth hormone).

### **9 DATA SAFETY MONITORING BOARD ANALYSIS**

There is no data and safety monitoring board for this study.

## 10 CHANGES TO PLANNED PROTOCOL ANALYSIS

- Primary analysis endpoint updated to percent change from Induction 1 (baseline visit) to Induction 2 (visit 7, week 4) in plasma epinephrine concentration after 30 minutes of induced hypoglycemia with plasma glucose <50 mg/dL.
- Absolute change from Induction 1 (baseline visit) to Induction 2 (visit 7, week 4) in plasma epinephrine concentration after 30 minutes of induced hypoglycaemia with plasma glucose <50 mg/dL moved from primary to secondary endpoint.
- The primary analyses will also be performed by diabetes duration category (<15 yrs, ≥15 yrs) and included in the secondary analyses.
- The secondary endpoint of describing subject reported severe hypoglycemic events when glucose meter reading <36 mg/dL was updated to glucose meter reading <50mg/dL. This was a typo in the protocol.
- The Per-Protocol Population definition has been updated to include subjects who participate in the study through day 27 with no major protocol deviations because treatment compliance data was not captured for the study.

## 12 LIST OF TABLES, FIGURES AND LISTINGS

The following table includes details of the tables, figures and listings (TFLs) for the study. Those marked with an asterisk (\*) are planned for the primary endpoint analysis and presentation of the accompanying safety analysis for that time period (See Section 8).

Table Number	Table Title	Shell Number (if repeat)
14.1.1.1*	Summary of Subject Disposition - All Subjects	
14.1.1.2*	Summary of Analysis Populations - All Randomized Subjects	
14.1.2*	Summary of Protocol Deviations - Intent-to-Treat Population	
14.1.3.1*	Summary of Demographic and Baseline Characteristics - Safety Population	
14.1.3.2*	Summary of Demographic and Baseline Characteristics - Intent-to-Treat Population	14.1.3.1
14.1.3.3*	Summary of Demographic and Baseline Characteristics - Per Protocol Population	14.1.3.1
14.1.4*	Summary of Medical History - Intent-to-Treat Population	
14.2.1.1*	Percent change from Induction 1 (Baseline visit) to Induction 2 (Visit 7, Week 4) in Plasma Epinephrine Concentration During Induced Hypoglycemia with PG <50 mg/dl Intent-to-Treat Population	
14.2.1.2*	Percent change from Induction 1 (Baseline visit) to Induction 2 (Visit 7, Week 4) in Plasma Epinephrine Concentration During Induced Hypoglycemia with PG <50 mg/dl Per Protocol Population	14.2.1.1
14.2.1.3*	Percent change from Induction 1 (Baseline visit) to Induction 2 (Visit 7, Week 4) in Plasma Epinephrine Concentration During Induced Hypoglycemia with PG <50 mg/dl, Sensitivity analysis 1* Per Protocol Population	14.2.1.1
14.2.1.4*	Percent change from Induction 1 (Baseline visit) to Induction 2 (Visit 7, Week 4) in Plasma Epinephrine Concentration During Induced Hypoglycemia with PG <50 mg/dl, Sensitivity analysis 2* Per Protocol Population	14.2.1.1
14.2.1.5*	Percent change from Induction 1 (Baseline visit) to Induction 2 (Visit 7, Week 4) in Plasma Epinephrine Concentration During Induced Hypoglycemia with PG <50 mg/dl, Sensitivity analysis 3* Per Protocol Population	14.2.1.1
14.2.2.1.1*	Absolute change from Induction 1 (Baseline visit) to Induction 2 (Visit 7, Week 4) in Plasma Epinephrine Concentration During Induced Hypoglycemia with PG <50 mg/dl Intent-to-Treat Population	14.2.1.1

Table Number	Table Title	Shell Number (if repeat)
14.2.2.1.2*	Absolute change from Induction 1 (Baseline visit) to Induction 2 (Visit 7, Week 4) in Plasma Epinephrine Concentration During Induced Hypoglycemia with PG <50 mg/dl Per Protocol Population	14.2.1.1
14.2.2.2.1*	Percent change from Induction 1 (Baseline visit) to Induction 2 (Visit 7, Week 4) in Plasma Epinephrine Concentration During Induced Hypoglycemia with PG <50 mg/dl by Duration of Diabetes Category Intent-to-Treat Population	14.2.1.1
14.2.2.2.2*	Percent change from Induction 1 (Baseline visit) to Induction 2 (Visit 7, Week 4) in Plasma Epinephrine Concentration During Induced Hypoglycemia with PG <50 mg/dl by Duration of Diabetes Category Per Protocol Population	14.2.1.1
14.2.2.3.1*	Change from Induction 1 (Baseline visit) in Counter Regulatory Hormones During Induced Hypoglycemia with PG <50 mg/dl - Intent-to-Treat Population	
14.2.2.3.2*	Change from Induction 1 (Baseline visit) in Counter Regulatory Hormones During Induced Hypoglycemia with PG <50 mg/dl - Per Protocol Population	14.2.2.3.1
14.2.2.4.1*	Change from Induction 1 (Baseline visit) in Counter Regulatory Hormones During Induced Hypoglycemia with PG <50 mg/dl – ANOVA - Intent-to-Treat Population	
14.2.2.4.2*	Change from Induction 1 (Baseline visit) in Counter Regulatory Hormones During Induced Hypoglycemia with PG <50 mg/dl – ANOVA - Per Protocol Population	14.2.2.4.1
14.2.2.5.1	Summary of Cumulative Glucose Infusion Rate (GIR) Required to Maintain Insulin-Induced Hypoglycemia Intent-to-Treat Population	
14.2.2.5.2	Summary of Cumulative Glucose Infusion Rate (GIR) Required to Maintain Insulin-Induced Hypoglycemia Per Protocol Population	14.2.2.5.1
14.2.2.6.1	Summary of Cumulative Insulin Infusion Rate Required to Maintain Insulin-Induced Hypoglycemia Intent-to-Treat Population	14.2.2.5.1
14.2.2.6.2	Summary of Cumulative Insulin Infusion Rate Required to Maintain Insulin-Induced Hypoglycemia Per Protocol Population	14.2.2.5.1
14.2.2.7.1.1	Change from Induction 1 (Baseline visit) in Average Neuroglycopenic Scores (ANS), Average Autonomic Scores (AAS) and Average Total Scores (ATS) with PG <70 mg/dl Intent-to-Treat Population	
14.2.2.7.1.2	Change from Induction 1 (Baseline visit) in Average Neuroglycopenic Scores (ANS), Average Autonomic	14.2.2.7.1.1

Table Number	Table Title	Shell Number (if repeat)
	Scores (AAS) and Average Total Scores (ATS) with PG <70 mg/dl Per Protocol Population	
14.2.2.7.2.1*	Change from Induction 1 (Baseline visit) in Average Neuroglycopenic Scores (ANS), Average Autonomic Scores (AAS) and Average Total Scores (ATS) with PG <50 mg/dl Intent-to-Treat Population	14.2.2.7.1.1
14.2.2.7.2.2*	Change from Induction 1 (Baseline visit) in Average Neuroglycopenic Scores (ANS), Average Autonomic Scores (AAS) and Average Total Scores (ATS) with PG <50 mg/dl Per Protocol Population	14.2.2.7.1.1
14.2.2.8.1.1	Summary of Overall Assessment of Hypoglycemia with PG <70 mg/dl Intent-to-Treat Population	
14.2.2.8.1.2	Summary of Overall Assessment of Hypoglycemia with PG <70 mg/dl Per Protocol Population	14.2.2.8.1.1
14.2.2.8.2.1	Summary of Overall Assessment of Hypoglycemia with PG <50 mg/dl Intent-to-Treat Population	14.2.2.8.1.1
14.2.2.8.2.2	Summary of Overall Assessment of Hypoglycemia with PG <50 mg/dl Per Protocol Population	14.2.2.8.1.1
14.2.2.9.1.1	Change from Baseline in CGM-Derived Hypoglycemia Parameters by Day - Intent-to-Treat Population	
14.2.2.9.1.2	Change from Baseline in CGM-Derived Hypoglycemia Parameters by Day - Per Protocol Population	14.2.2.9.1.1
14.2.2.9.2.1	Change from Baseline in CGM-Derived Hypoglycemia Parameters by Week - Intent-to-Treat Population	14.2.2.9.1.1
14.2.2.9.2.2	Change from Baseline in CGM-Derived Hypoglycemia Parameters by Week - Per Protocol Population	14.2.2.9.1.1
14.2.2.10.1*	Change from Induction 1 (Baseline visit) in Gold Scale Assessment of Hypoglycemia Unawareness - Intent-to-Treat Population	
14.2.2.10.2*	Change from Induction 1 (Baseline visit) in Gold Scale Assessment of Hypoglycemia Unawareness - Per Protocol Population	14.2.2.10.1
14.3.1.1*	Overview of Adverse Events - Safety Population	
14.3.1.2*	Summary of Treatment-Emergent Adverse Events by System Organ Class, Preferred Term - Safety Population	
14.3.1.3	Summary of Treatment-related Treatment-Emergent Adverse Events by System Organ Class, Preferred Term - Safety Population	14.3.1.2
14.3.1.4*	Summary of Serious Treatment-Emergent Adverse Events by System Organ Class, Preferred Term - Safety Population	14.3.1.2
14.3.1.5	Summary of Treatment-Emergent Adverse Events Leading to Study Discontinuation by System Organ Class, Preferred Term - Safety Population	14.3.1.2

Table Number	Table Title	Shell Number (if repeat)
14.3.1.6	Summary of Serious Adverse Events Leading to Death by System Organ Class, Preferred Term - Safety Population	14.3.1.2
14.3.1.7	Summary of Serious Adverse Events Leading to Study Discontinuation by System Organ Class, Preferred Term - Safety Population	14.3.1.2
14.3.1.8.1	Summary of Treatment-Emergent Adverse Events by System Organ Class, Preferred Term and Severity - Safety Population	
14.3.1.8.2	Summary of Treatment-related Treatment-Emergent Adverse Events by System Organ Class, Preferred Term and Severity - Safety Population	14.3.1.8.1
14.3.1.9*	Summary of Treatment-Emergent Adverse Events by System Organ Class, Preferred Term and Relationship to Study Drug - Safety Population	
14.3.2.1	Summary of Deaths - Safety Population	
14.3.2.2*	Summary of Serious Adverse Events - Safety Population	
14.3.2.3	Summary of Treatment-Emergent Adverse Events Leading to Study Discontinuation - Safety Population	
14.3.4.1.1	Summary of Clinical Chemistry Results - Safety Population	
14.3.4.2.1	Summary of Clinical Hematology Results - Safety Population	14.3.4.1.1
14.3.4.1.2	Summary of Clinical Chemistry Results: Shift from Baseline - Safety Population	
14.3.4.2.2	Summary of Clinical Hematology Results: Shift from Baseline Safety Population	14.3.4.1.2
14.3.5.1	Summary of Treatment Exposure Safety Population	
14.3.6.1	Summary of Vital Signs - Safety Population	
14.3.7.1.1	Summary of Overall ECG Interpretation - Safety Population	
14.3.7.1.2	Summary of Overall ECG Interpretation: Shift from Baseline - Safety Population	
14.3.7.2.1	Summary of Local Tolerability – Injection Site VAS Discomfort Score - Safety Population	
14.3.7.2.2	Summary of Local Tolerability – Injection Site Discomfort at 10 Minutes Following the Injection of Study Drug - Safety Population	
14.3.7.2.3	Summary of Local Tolerability – Draize Scale - Safety Population	
14.3.7.2.4	Summary of Local Tolerability – Draize Scale: Shifts from Week 1 - Safety Population	
14.3.8.1	Summary of Prior Medications - Safety Population	

Table Number	Table Title	Shell Number (if repeat)
14.3.8.2*	Summary of Concomitant Medications - Safety Population	14.3.8.1

Figure Number	Figure Title	Shell Number (if repeat)
14.2.2.1*	Observed Values and Change from Induction 1 (Baseline visit) in Counter Regulatory Hormones Over Time - Intent-to-Treat Population	
14.2.1.2*	Observed Values and Change from Induction 1 (Baseline visit) in Counter Regulatory Hormones Over Time Per Protocol Population	14.2.2.1
14.2.2.1	Cumulative Glucose Infusion Rate (GIR) Required to Maintain Insulin-Induced Hypoglycemia Over Time - Intent-to-Treat Population	
14.2.2.2	Cumulative Glucose Infusion Rate (GIR) Required to Maintain Insulin-Induced Hypoglycemia Over Time - Per Protocol Population	14.2.2.1
14.2.3.1	Cumulative Insulin Infusion Rate Required to Maintain Insulin-Induced Hypoglycemia Over Time - Intent-to-Treat Population	14.2.2.1
14.2.3.2	Cumulative Insulin Infusion Rate Required to Maintain Insulin-Induced Hypoglycemia Over Time - Per Protocol Population	14.2.2.1
14.2.4.1.1	Average Neuroglycopenic Scores (ANS), Average Autonomic Scores (AAS) and Average Total Scores (ATS) with PG <70 mg/dl Over Time - Intent-to-Treat Population	
14.2.4.1.2	Average Neuroglycopenic Scores (ANS), Average Autonomic Scores (AAS) and Average Total Scores (ATS) with PG <70 mg/dl Over Time - Per Protocol Population	14.2.4.1.1
14.2.4.2.1*	Average Neuroglycopenic Scores (ANS), Average Autonomic Scores (AAS) and Average Total Scores (ATS) with PG <50 mg/dl Over Time - Intent-to-Treat Population	14.2.4.1.1
14.2.4.2.2*	Average Neuroglycopenic Scores (ANS), Average Autonomic Scores (AAS) and Average Total Scores (ATS) with PG <50 mg/dl Over Time - Per Protocol Population	14.2.4.1.1
14.2.5.1.1	CGM-Derived Hypoglycemia Parameters by Day - Intent-to-Treat Population	
14.2.5.1.2	CGM-Derived Hypoglycemia Parameters by Day - Per Protocol Population	14.2.5.1.1

Figure Number	Figure Title	Shell Number (if repeat)
14.2.5.2.1	CGM-Derived Hypoglycemia Parameters by Week - Intent-to-Treat Population	14.2.5.1.1
14.2.5.2.2	CGM-Derived Hypoglycemia Parameters by Week - Per Protocol Population	14.2.5.1.1
14.2.6.1	Gold Scale Assessment of Hypoglycemia Unawareness Over Time - Intent-to-Treat Population	
14.2.6.2	Gold Scale Assessment of Hypoglycemia Unawareness Over Time - Per Protocol Population	14.2.6.1

Listing Number	Listing Title	Shell Number (if repeat)
16.1.7*	Randomization of Subjects Intent-to-Treat Population	
16.2.1.1*	Subject Disposition All Subjects	
16.2.1.2*	Subject Eligibility and Inclusion/Exclusion Criteria Assessment All Subjects	
16.2.2.1*	Protocol Deviations All Subjects	
16.2.2.2	Major Protocol Deviations All Subjects	
16.2.3*	Analysis Populations All Randomized Subjects	
16.2.4.1*	Subject Demographic and Baseline Characteristics Intent-to-Treat Population	
16.2.4.2*	Medical History Intent-to-Treat Population	
16.2.4.3*	Prior and Concomitant Medications Safety Population	
16.2.5.1	Study Drug Administration Intent-to-Treat Population	
16.2.5.2	Euglycemic Baseline and Hypoglycemia Induction Intent-to-Treat Population	
16.2.5.3*	Plasma Blood Glucose during Euglycemic Maintenance, Hypoglycemia Induction and Stabilization, and Normalization to Euglycemia All Subjects	
16.2.5.4	Plasma Blood Glucose Levels from Plasma Glucose Screener Intent-to-Treat Population	
16.2.6.1	Subject Insulin Diary Safety Population	
16.2.6.2.1	Interstitial Glucose Parameters During CGM Monitoring All Subjects	
16.2.6.3.1	Average Glucose Infusion Rate to Maintain Glucose at 50 mg/dL for the first 30 minutes after 50 mg/dL Achieved during Hypoglycemia Stabilization All Subjects	
16.2.6.3.2	Cumulative Glucose Infusion to Maintain Glucose at 50 mg/dL for the first 30 minutes after 50 mg/dL Achieved during Hypoglycemia Stabilization All Subjects	
16.2.6.4.1.1	Hypoglycemia Symptom Questionnaire Responses After Achieving Plasma Glucose of < 70 mg/dL All Subjects	
16.2.6.4.1.2*	Hypoglycemia Symptom Questionnaire Responses After Achieving Plasma Glucose of < 50 mg/dL All Subjects	

Listing Number	Listing Title	Shell Number (if repeat)
16.2.6.4.2.1	Average Neuroglycopenic, Autonomic and Total Symptom Scores After Achieving Plasma Glucose of < 70 mg/dL All Subjects	
16.2.6.4.2.2*	Average Neuroglycopenic, Autonomic and Total Symptom Scores After Achieving Plasma Glucose of < 50 mg/dL All Subjects	
16.2.6.4.3.1	Overall Assessment of Hypoglycemia After Achieving Plasma Glucose of < 70 mg/dL All Subjects	
16.2.6.4.3.2	Overall Assessment of Hypoglycemia After Achieving Plasma Glucose of < 50 mg/dL All Subjects	
16.2.6.4.4	Gold Scale of Hypoglycemia Unawareness All Subjects	
16.2.7*	Adverse Events All Patients	
16.2.8.1*	Hormones and Counter Regulatory Hormone Response All Patients	
16.2.8.2	Serum Concentration of Glucagon during CSGI Treatment All Patients	
16.2.8.3	Serum and Plasma Concentration of Glucagon Antibodies All Patients	
16.2.8.4	Clinical Laboratory Results: Hematology All Patients	
16.2.8.5	Laboratory Results: Chemistry, Complete Metabolic Panel Safety Population	
16.2.8.6	Laboratory Results: Drug Screen All Patients	
16.2.8.7	Listing of Laboratory Results: Serology Intent-to-Treat Population	
16.2.8.8	Urine Pregnancy Test Results All Patients	
16.2.9.1	Injection Site Discomfort - Visual Analog Scale (VAS) Safety Population	
16.2.9.2	Injection Site Discomfort - Injection Site Discomfort Description and Duration Questionnaire Safety Population	
16.2.9.3	Injection Site Reactions - Draize Scale Safety Population	
16.2.9.4	Vital Signs and Weight Safety Population	
16.2.9.5	12-Lead Electrocardiogram (ECG) Interpretation Safety Population	
16.2.9.6	Physical Examinations Safety Population	
16.2.10	Comments All Patients
